Table II. Clinical grade based on a score out of 100 points for working and 80 points for non-working patients (see text)

Working before injury	Not working before injury	Grade
> 85	> 70	Excellent
70 to 84	55 to 69	Good
55 to 69	45 to 54	Fair
< 55	< 45	Poor

STUDY POPULATION

The study population will be patients aged 18-80 with a lateral compression type pelvic fracture that go on to receive operative or non-operative treatment of the injury.

Inclusion Criteria:

1. Patients that have one of the following pelvic fractures (includes bilateral sacral fractures): lateral compression type 1, lateral compression type 2, lateral compression type 3.
2. Patients between 18 and 80 years of age, inclusive.
3. Patient has reached skeletal maturity.
4. The patient's pelvic fracture is a result of trauma (includes polytraumatized patients).
5. The patient/family/guardian is English-speaking.
6. The patient's surgeon agrees to randomization (the patient is amendable to either operative or non-operative treatment).
7. Patient enrollment and, if applicable, patient randomization, can occur within 96 hours post injury.

Exclusion Criteria:

Patients who satisfy any of the following exclusion criteria will be ineligible for enrollment in the study:

1. The patient has prior surgical hardware in place that precludes intervention.
2. If the patient's pelvic fracture is classified as LC1 and the associated sacral fracture is incomplete as indicated by failure to violate both the anterior and posterior cortex.
3. The patient received prior surgical intervention for his/her current pelvic injury.
4. The patient has sacral morphology that precludes percutaneous fixation.
5. The patient is non-ambulatory due to an associated spinal cord injury.
6. The patient was non-ambulatory pre-injury.
7. The patient is currently pregnant.
8. The patient is enrolled in another study that does not allow co-enrollment.
9. The patient is likely to have severe problems maintaining follow up.

ADJUDICATING ELIGIBILITY

To ensure consistency in the application of inclusion criteria and in the classification of injuries, all fractures will be re-evaluated by a surgeon in Shock Trauma who is not treating the patient. These evaluations will be based on slides of AP and lateral x-rays. Each case will be independently reviewed. The non-treating surgeon will convene to discuss the case if there is disagreement regarding eligibility or classification of the injury to resolve differences of opinion.

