Patients enrolled in the operative treatment group will undergo surgical intervention for their pelvic fracture. The surgeon will decide the best surgical technique as per standard of care for the patient's injury. The patient will mobilize as per the surgeon's instructions and x-rays will be taken at follow-up clinic appointments to determine if the injury is healing properly. If additional surgery is required or other complications arise, this will be recorded within the study follow-up forms.

CLINICAL EVALUATION

A summary of the clinical evaluations is outlined below and can also be found in Appendix B.

Medical Record Review

During the index hospitalization, information about the participant (medical history, height and weight, etc.) and the participant's injuries and hospital stay will be collected, including mechanism, presence of and severity of other orthopaedic and non-orthopaedic injuries, procedures done in the hospital, overall (and ICU) length of stay, time to mobilization (bed to chair) in physical therapy, pain medication administration, and discharge disposition.

Assessment of Study Injuries

The extent and severity of the pelvic injury will be prospectively assessed by the treating surgeon after initial x-rays are taken. The following injury characteristics will be collected:

- Lateral compression type classification of the pelvic fracture
- Skin defect associated with the pelvic injury
- Muscle and tendon injury associated with the pelvic injury
- Deep vein injury associated with the pelvic injury
- Nerve injury associated with the pelvic injury

Assessment of Study Injury Treatment

For participants undergoing operative treatment, the following information will be obtained:

- Type of fracture stabilization
- Type and timing of fixation revisions
- Limb Complications (type, severity, treatment)

Assessments at 2 weeks, 6 weeks, 3 months, and 1 year post injury

- Complications since last follow-up (type, severity, treatment)
- Assessment of fracture healing
- Weight bearing status and ambulation
- Use of ambulatory devices
- Pain assessment
- Narcotic use assessment

X-rays

AP and lateral x-rays at admission, post-operative treatment (when applicable), and at the 2 week, 6 week, 3 month and 1 year follow-ups will be obtained. These x-rays are obtained per standard of care.

PARTICIPANT INTERVIEWS

A summary of the participant interviews performed are outlined below and can also be found in Appendix D.

Baseline Hospital Interview

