During the index hospitalization, participants will be asked about the following:

- Age, gender, race and ethnicity, and education
- Smoking history
- Previous injuries (specifically pelvis or back)
- Pain medication usage prior to this injury
- Work and health status prior to this injury
- General and pelvic function prior to this injury

Follow-up Interviews

At 2 weeks, 6 weeks, 3 months, and 1 year following their injury, participants will be asked about the following:

- Any re-hospitalization or outpatient surgery since the last visit for any reason related to his/her pelvic injury
- Rehabilitation received
- Pain medication usage
- Work Status – Work Productivity and Activity Impairment
- Pain – Brief Pain Inventory
- Health Status – VR-12
- Pelvic Function – Majeed Pelvic Score

STUDY SCHEDULE

Screening and Consent

All patients between the ages of 18 and 80 (inclusive) with a lateral compression type pelvic fracture will be screened for eligibility by the research coordinator or research team members in close coordination with the surgeon investigators. Screening will typically occur within the first day after hospital admission. An eligibility checklist form will be completed on every potentially eligible participant and entered onto the electronic data capture system. The treating surgeon will be available via pager to answer questions regarding study eligibility. When the treating surgeon is not available, the study PI will be available to page. Contact information for the PI and alternate contact is available in Appendix A. In most cases, questions should be resolved at this level.

Once eligibility has been confirmed, the informed consent process will be completed by the research coordinator or research team member and attending surgeon. Patients will be approached about potential participation in the study as soon as is feasible following determination of eligibility. It will be important to enroll these participants as soon as possible to prospectively collect information about their injury and its treatment.

Following completion of informed consent, the participant's study injury characteristics will be further adjudicated by a non-treating surgeon as described in the Adjudicating Eligibility Section of this protocol. Participants with injuries that are not judged eligible for inclusion will be withdrawn from the study.

Enrollment/Baseline

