
We took two critical steps to understand the potential for biased treatment estimates from pooling the results from the randomized and non-randomized participants. First, we performed sensitivity analyses to separately examine the results for the randomized and non-randomized cohorts. These analyses suggested similar (or even larger) estimated treatment benefits from surgery within the RCT data. Second, we included willingness to be randomized as a potentially confounding variable in our final analysis models, despite there being no evidence that it affected treatment.

[figure not shown]
The ability to assess the probability of different magnitudes of treatment benefit is a unique characteristic of Bayesian data analysis, and is not possible with traditional non-Bayesian statistical hypothesis testing. Despite this inherent difference in statistical principles, it should be noted that the average treatment benefits reported from our Bayesian analysis are nearly identical to the results obtained using traditional multilevel linear regression models (results not reported).

Additional results from the described analyses, that were not included in the main article, are provided below.

[figure not shown]
**Posterior probability of reduced pain.** Posterior probability of reduced pain with operative treatment within 12 weeks of injury.

[figure not shown]
**Mean pain stratified between randomized and nonrandomized patients.** The mean Brief Pain Inventory scores and 95% credible intervals within the initial 12-weeks of injury for minimally displaced complete lateral compression pelvis fracture patients. The patients are stratified based on their study type (randomized trial versus observation) and treatment type (operative versus nonoperative treatment). The pain scores are adjusted for the study type, prior narcotic use, and narcotic use at each time point.

**Posterior probability of improved function.** Posterior probability of improved function, measured with the Majeed score, with operative treatment within 12 weeks of injury.

**Mean function stratified between randomized and nonrandomized patients.** The mean Majeed scores and 95% credible intervals within the initial 12-weeks of injury for minimally displaced complete lateral compression pelvis fracture patients. The patients are stratified based on their study type (randomized trial versus observation) and treatment type (operative versus nonoperative treatment).

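### For LC1 fractures, adjudication can withdraw a consented patient on a two-cortex criterion, yet it is stated to rest on AP and lateral films, which are unlikely to settle that criterion reliably

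*Protocol*

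**What the plan says.** Protocol, Study Population, Exclusion Criteria, item 2: an LC1 patient is ineligible when "the associated sacral fracture is incomplete as indicated by failure to violate both the anterior and posterior cortex". The item does not apply to LC2 or LC3.

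Protocol, Adjudicating Eligibility: a Shock Trauma surgeon who is not treating the patient re-evaluates all fractures. On the evidence for that review: "These evaluations will be based on slides of AP and lateral x-rays". A discussion follows "if there is disagreement regarding eligibility or classification of the injury to resolve differences of opinion".

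Protocol, Study Schedule, Screening and Consent: "Following completion of informed consent, the participant's study injury characteristics will be further adjudicated by a non-treating surgeon". The consequence is then stated: "Participants with injuries that are not judged eligible for inclusion will be withdrawn from the study".

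Protocol, Clinical Evaluation: the injury is "prospectively assessed by the treating surgeon after initial x-rays are taken", and five characteristics are listed for collection. Completeness of the sacral fracture is not one of them. The X-rays subsection names "AP and lateral x-rays at admission, post-operative treatment (when applicable), and at the 2 week, 6 week, 3 month and 1 year follow-ups". In Appendix B the only imaging row is for pelvic x-rays. Neither the protocol text nor the SAP mentions CT.

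SAP, Statistical Analysis, figure captions: the analysed patients are described as "minimally displaced complete lateral compression pelvis fracture patients".

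**The concern.** The criterion asks whether a fracture line crosses two surfaces that lie one behind the other. An AP beam travels from front to back, so it lays the anterior and posterior sacral cortices on top of each other. A lateral beam travels from side to side, so it lays the injured side over the other side. A line through one cortex and a line through both could therefore look alike on either view. This is geometry, not a finding reported in the documents.

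Two errors could follow, both confined to LC1. An incomplete fracture that the protocol means to exclude could be passed and, if such patients benefit less from surgery, dilute the treatment contrast. A complete fracture could be read as incomplete and an eligible, consented patient withdrawn. The adjudicator may also work from less than the treating surgeon had, so that a disagreement reflects the imaging available and not the injury. Completeness matters to the reported result because the SAP uses it to describe its population.

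**Working it through.** **Step 1. The rule against the criterion.**

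| Element | Where | Content |
|---|---|---|
| Criterion | Exclusion 2 | LC1 only; both sacral cortices |
| First application | Screening and Consent | Research staff with the surgeon investigators; imaging not restricted |
| Independent check | Adjudicating Eligibility | All fractures; AP and lateral films |
| Consequence | Screening and Consent | Withdrawal after consent |
| Listed record | Clinical Evaluation | Five items; completeness absent |
| Reported population | SAP captions | Complete fractures |

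The imaging for the check is stated, not merely left open, and no passage widens it. No reading rule for the two-cortex question is given.

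**Step 2. Does adjudication reach Exclusion 2?** The section's opening aim concerns inclusion criteria and classification. The same paragraph then refers to disagreement over eligibility, and Screening and Consent withdraws patients whose injuries are not judged eligible. Coverage is therefore implied. If it were not intended, the text would contain no independent check of completeness.

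**Step 3. Reproduce the sample size.** Inputs from the protocol, Data Analysis: means 5.7 and 4.56, so the difference is 5.7 − 4.56 = 1.14; SD 2.3; 65 per arm; 5% level; 80% power. Sidedness is not stated.

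- Standardised difference: 1.14 / 2.3 = 0.496.
- Two-sample t-test, two-sided 5%, 80% power: 64.87 per arm, rounded up to 65, or 130 in total. This matches the protocol.
- Power with 65 per arm: 80.1%.
- A one-sided test would need 102 in total, so the two-sided reading is the one that reproduces.

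**Step 4. Illustrate dilution.** Let f be the share of all enrolled patients who are truly ineligible, equal in both arms, and assume that they gain nothing from surgery. The expected difference becomes 1.14 × (1 − f). The SD is held at 2.3.

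| f (assumed) | Difference | Power, 65 per arm (t-test) |
|---|---|---|
| 0% | 1.14 | 80.1% |
| 10% | 1.026 | 71.4% |
| 20% | 0.912 | 61.2% |

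The normal approximation gives 80.7%, 72.0% and 61.8%.

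Because only LC1 is affected, f = (LC1 share of those enrolled) × (share of those LC1 patients who are truly incomplete). The documents give neither factor. If LC1 made up half of enrolment (assumed), f = 10% would require 20% of LC1 patients to be misclassified, since 0.5 × 0.2 = 0.1.

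**Step 5. Limits.** These figures belong to the protocol's two-group design calculation. The SAP's primary analysis is a Bayesian longitudinal model over 12 weeks, so they do not describe that model's precision.

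**The case against.** The strongest reply is that the premise is radiological and no passage states it. That stands: the documents do not say that plain films fail to show both cortices, and they report no reader agreement. A reader might infer that the criterion is unmeasurable, or that films can never show it. The text does not support either. What can be said is that two superimposing views are a weak basis for this particular question.

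Second, adjudication is a second look. Screening comes first and its imaging is not restricted. The phrase about initial x-rays under Assessment of Study Injuries gives timing, not the sole evidence. Disagreements are discussed before they are settled. All of this stands, and it means that one adverse reading need not end a patient's participation. It does not repair the check itself, which may overrule a better-informed judgement on the evidence that the protocol assigns to it.

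Third, silence is not absence. The SAP divides patients by displacement at 5 mm, although displacement is not among the five listed injury characteristics either, so that list is not a full record of what was assessed. The case report forms (Appendix D) are not in the supplied text and may capture completeness. This stands, so a reader should not conclude that completeness was never recorded or that the SAP's description of its patients is wrong. The SAP simply does not say how completeness was determined.

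Fourth, if CT was common in routine care, surgeons may already have screened out most incomplete fractures, and contamination could be small. This is fair, and it is why the power figures are illustrative. Under the same assumption, the better images existed and the adjudication rule did not call for them.

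**Conclusion.** The concern holds for LC1 fractures. The protocol states an imaging basis for adjudication that is ill-suited to the criterion being adjudicated, and attaches withdrawal to the outcome. This rests on the wording of the protocol and on projection reasoning, not on any accuracy figure in the documents.

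The size of the effect is unknown. The fall in power from 80% to about 71% or 61% depends on two assumptions without a source: that 10% or 20% of all enrolled patients were ineligible, and that they had no benefit. A reader might take these figures as evidence that the trial was diluted, but nothing in the documents shows that any patient was misclassified. Confidence is medium, and the change is worth making because it costs little.

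**What to change.** - **Adjudication sentence.** Amend it so that evaluations use all admission imaging already obtained in routine care, including any CT. No new imaging is requested.
- **Case report form.** Record the completeness result and the modality on which it was judged, with not assessable as a permitted recorded value. This value documents the evidence only; Exclusion 2 is unchanged. If the existing forms already hold these items, citing them is enough.
- **Sensitivity analysis.** Repeat the main pain analysis with the LC1 patients restricted to those whose completeness was confirmed on cross-sectional imaging, keeping LC2 and LC3 patients as they are.

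The SAP is written in the past tense, with results. For this trial, the practical steps are therefore to report which imaging the adjudicators used, to re-read existing cross-sectional images where they are available, and to add the sensitivity analysis.

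The cost is sharing scans from the second site with the Shock Trauma adjudicator, the added form entries, and one further analysis. The restricted analysis will be smaller and less precise by an amount that depends on how many LC1 patients had cross-sectional imaging, which the documents do not give.

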There is evidence in the literature to support both operative and non-operative treatment of patients with LC1 or LC2 pelvic fractures. There is conflicting evidence that surgical stabilization decreases acute pain and narcotic requirements, although patients are often counseled to that effect. We propose to prospectively randomize patients with lateral compression type pelvic fractures to non-operative versus operative treatment and track which group has less pain, less need for narcotic pain medications, and who mobilizes with physical therapy faster.

POTENTIAL RISKS

If the patient is randomized to operative treatment, he/she will be exposed to all of the risks associated with surgery under a general anesthetic including but not limited to: prolonged intubation, heart attack, stroke and death. These risks are extremely rare and will be explained to the patient and/or family by the anesthesia team, and a separate anesthesia consent will be obtained. The risks of the surgical procedure are rare but include: infection, wound break down, failure of hardware, and neurologic injury. A separate surgical consent will be provided to go into more detail of the risks of the procedure.

The risk of non-operative treatment is displacement of fracture with possible need for surgical intervention or prolonged protected weight-bearing. This is unlikely but will be monitored closely, as per our standard of care.

While the intake questionnaire and information gathered is of a sensitive nature (income, narcotic use, pain and psychiatric history) and it might cause the patient some discomfort to answer truthfully, all information will be kept confidential and no identifiers will be used in publication.

While every attempt will be made to keep all information confidential and the master link between the patient study number and personal identifiers will be destroyed at the completion of the study, there remains a risk of the potential for the loss/breach of confidentiality. This risk will be minimized by storing all paper questionnaires in a secure, locked location and all electronic data will be password protected.

There may be risks in this study which are not yet known.

POTENTIAL BENEFITS

While there are no direct benefits to patients participating in the study (except for those that may accrue from closer clinical observation as a study patient), participation may help determine the best treatment for lateral compression type pelvic fractures in the future.

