Once consented into the study, baseline data regarding participant characteristics, injury characteristics, fracture classification and medical history/co-morbidities will be collected. Characteristics about the hospital course and treatment received will also be collected. A brief interview will be conducted with the participant. All data will be recorded on the paper Case Report Form (CRF) and entered into the electronic data capture system.

Follow-up

Participants will return for follow-up visits at 2 weeks, 6 weeks, 3 months, and 1 year post injury. Participants will undergo a clinical evaluation by the treating surgeon and be interviewed by the research coordinator or research team member. These visits tend to mirror clinic visits per standard of care, however there may be some circumstances where patients are unwilling to return to the clinic. In these situations the research coordinator or research team member may obtain as much visit data as possible by phone and/or medical record review to prevent loss of important study information. All data will be recorded on the paper Case Report Form (CRF) and entered into the electronic data capture system.

Retention

Every effort will be made to retain participants in the study. We will keep participants engaged through use of study updates during non-study clinic appointments, and reminder calls/letters for upcoming appointment visit window timeframes.

Visit Windows

Each visit will have an interval of time surrounding the ideal date for the visit during which the visit may be completed and the data included in the trial database. This interval is approximately 1 week before or after the ideal date for the 2 week and 6 week follow-up appointments, and 2 weeks before or after the ideal date for a visit for the 3 month and 1 year follow-up appointments. Study data will still be collected even if the visit falls out of the ideal window of time.

ASSESSMENT OF SAFETY

The study will monitor and report adverse events to ensure participant safety. Each participating site is responsible for ensuring that all local IRB requirements for reporting adverse events (both internal and external) are met.

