The safety monitor (SM) is responsible for providing medical guidance and overseeing participant safety for the study. The SM participates in determining the course of action necessary to meet safety goals and objectives. This is achieved through the review of Serious Adverse Event reports; resolving safety issues; and interacting with the Principal and Sub-Investigators at each site.

Reportable New Information (RNI)

The following information must be reported to the coordinating center IRB within FIVE (5) business days of the investigator becoming aware of the information (please note that a separate RNI must be completed and submitted for each problem/event/report):

- Information that indicates a new or increased risk. For example:
 - New information (e.g., an interim analysis, safety monitoring report, publication in the literature, sponsor report, or investigator finding) indicates an increase in the frequency or magnitude of a previously known risk, or uncovers a new risk
 - An investigator brochure, package insert, or device labeling is revised to indicate an increase in the frequency or magnitude of a previously known risk, or describe a new risk
 - Withdrawal, restriction, or modification of a marketed approval of a drug, device, or biologic used in the research protocol
 - Protocol violation that harmed subjects or others or that indicates subjects or others might be at increased risk of harm
 - Complaint of a subject that indicates subjects or others might be at increased risk of harm or at risk of a new harm
 - Any changes significantly affecting the conduct of the research
- Any harm experienced by a subject or other individual which in the opinion of the local investigator is unexpected and at least probably related to the Human Research procedures and suggests that the research places subjects or others at a greater risk of harm than was previously known or recognized
 - A harm is “unexpected” when its specificity or severity are inconsistent with risk information previously reviewed and approved by the IRB in terms of nature, severity, frequency, and characteristics of the study population
 - A harm is “at least probably related to the Human Research procedures” if in the opinion of the local investigator, the research procedures more likely than not caused the harm (greater than 50% probability)

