- Non-compliance with the federal regulations governing human research or with the requirements or determinations of the IRB, or an allegation of such non-compliance
- Failure to follow the protocol due to the action or inaction of the investigator or research staff
- Breach of confidentiality
- Change to the protocol taken without prior IRB review to eliminate an apparent immediate hazard to a subject

- Incarceration of a subject in a study not approved by the IRB to involve prisoners
- Complaint of a subject that cannot be resolved by the research team
- Premature suspension or termination of the research by the sponsor or the investigator
- Unanticipated adverse device effect (any serious adverse effect on health or safety or any life-threatening problem or death caused incidence in the investigational plan or application – including a supplementary plan or application – or any other unanticipated serious problem associated with a device that relates to the rights, safety, or welfare of subjects)
- Audit, inspection, or inquiry by a federal agency
- Written reports of study monitors

Serious Adverse Event (SAE)

Serious Adverse Events may be discovered during regularly scheduled visits or through unscheduled participant contacts between visits. SAEs will be managed according to the medical judgment of the treating physician and source documentation will be maintained (e.g. laboratory and/or radiology reports, clinical notes, discharge summaries). The following are the categories considered for a serious adverse event and must be reported to the IRB during the continuing review process:

- Serious, unexpected, not related
 - Is unexpected, in terms of nature, severity, or frequency, given the research procedures that are described in the protocol and informed consent document and the characteristics of the participants eligible for the study
 - e.g. Death not due to study participation
- Serious, expected, related
 - Is related or possibly related to treatment/procedures under study; possibly related means there is a reasonable possibility that the incident, experience, or outcome may have been caused by the study procedures or treatments
- Serious, expected, not related

Study patients who experience an SAE will be followed until resolution of the event and a final report will be submitted to the safety monitor and IRB. Please note that SAE's and RNI's may overlap and a single event may be classified under both conditions.

DATA ANALYSIS

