APPENDIX B: DATA COLLECTION SCHEDULE

Assessment	Screen / Enroll	Pre-Rand. Base	Post-Rand. Base	96-hour	2 week	6 week	3 month	1 year
Pelvic x-rays	X							
Informed Consent	X							
HIPAA	X							
Stratification Levels (AF03)								
Intubation Status (at time of consent)		X						
Prescription Pain Medication Usage (during month prior to pelvic injury)		X						
Patient Intake (CRF01)								
Demographics (age, gender, race/ethnicity, education)			X					
Smoking History			X					
Previous Injuries			X					
Pre-injury Pain Medication Usage			X					
Pre-injury Work Status (WPAI:SHP)			X					
Pre-Injury Health Status (VR-12)			X					
Pre-Injury Pelvic Function (Majeed Pelvic)			X					
Index Hospitalization - Clinical Intake (CRF02)								
Length of Stay & Discharge Disposition			X					

Assessment	Screen / Enroll	Pre-Rand. Base	Post-Rand. Base	96-hour	2 week	6 week	3 month	1 year
ICU Length of Stay			X					
Date/Time & Mechanism of Injury			X					
Height & Weight			X					
Medical History			X					
Time to Mobilization (Bed to Chair)			X					
Narcotic Use			X					
OR Trip(s) Identification			X					
Classification of All Injuries			X					
Study Injury Characteristics			X					
Study Treatment Characteristics			X					
Patient Follow-Up (CRF03 & CRF04)								
Brief Pain Inventory (BPI)				X	X	X	X	X
Re-hospitalizations or Surgeries					X	X	X	X
Physical Therapy Tracking					X	X	X	X
Post-Injury Pain Medication Usage					X	X	X	X
Post-Injury Work Status (WPAI: SHP)					X	X	X	X
Post-Injury Health Status (VR-12)					X	X	X	X
Post-Injury Pelvic Function (Majeed Pelvic)					X	X	X	X
Clinical Follow-Up (CRF05)								
Ambulation & Weight Bearing Status					X	X	X	X
Pain Medication Usage					X	X	X	X
Fracture Healing Status					X	X	X	X
Complications (type, severity, treatment)					X	X	X	X

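### The follow-up interview asks only about hospital stays and surgery related to the pelvic injury, which is narrower than the data collection schedule and the serious adverse event section

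*Protocol*

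**What the plan says.** The Follow-up Interviews list in the protocol's Participant Interviews section applies at 2 weeks, 6 weeks, 3 months and 1 year. Its only item on hospital stays is "Any re-hospitalization or outpatient surgery since the last visit for any reason related to his/her pelvic injury".

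Appendix B lists the corresponding row, under the patient follow-up forms and at the same four time points, as "Re-hospitalizations or Surgeries", with no qualifier.

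The Serious Adverse Event section names three categories that go to the IRB at continuing review. Two of the three are for events judged not related; one of these reads "Serious, expected, not related".

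The Potential Risks section lists, among the risks of surgery under general anesthesia, "prolonged intubation, heart attack, stroke and death".

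At the same four visits the Clinical Evaluation section also records "Complications since last follow-up (type, severity, treatment"), with no limit on relatedness. The Follow-up paragraph of the Study Schedule divides the work: "Participants will undergo a clinical evaluation by the treating surgeon and be interviewed by the research coordinator or research team member".

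**The concern.** One protocol gives the same piece of information two scopes. Read literally, the interview item leaves out unrelated admissions, which the serious adverse event section expects to see. The qualifier also refers to the injury. A participant admitted to another hospital with a stroke some weeks after pelvic fixation could honestly say that the stay had nothing to do with the pelvic injury, although the protocol lists stroke as a risk of the operation.

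What is at stake is the completeness of safety information. The safety monitor works from serious adverse event reports and can review only events that someone has elicited. No efficacy result is at stake: re-hospitalization is not a listed endpoint, and the SAP describes no between-arm safety comparison.

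**Working it through.** The plan states no figure on this point, so the check is to set the sections side by side and ask which route would bring a later, apparently unrelated admission to light.

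1. **Scope of the item.** The interview list is restricted to the pelvic injury. The Appendix B row is unrestricted. The serious adverse event categories explicitly include unrelated events. The interview wording is the narrowest of the three.

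2. **Fit to the named risks.** The Potential Risks section ties heart attack and stroke to surgery under general anesthesia. The interview item mentions neither surgery nor anesthesia as a cause. Its reference to outpatient surgery is to a type of event.

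3. **Other routes of capture.**
   - *Complications item.* It is unrestricted and recorded at all four visits, so it is a real second route. The term is not defined, however, and the item belongs to the clinical evaluation done by the treating surgeon. The Description of the Study Design allows follow-up by phone, with an examination only where applicable.
   - *Record review.* For participants who do not come back to clinic, the Study Schedule offers phone contact, record review or both. Review is therefore optional, and nothing calls for records from other hospitals.
   - *Unscheduled contacts.* The serious adverse event section says events may surface at visits or between them. That describes where they may be found and adds no question to the participant. Appendix B has no separate adverse event row.
   - *Index-stay records.* These cover early perioperative events but not later admissions.

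4. **Recall interval.** From 2 to 6 weeks is 4 weeks. From 6 weeks to 3 months (about 13 weeks) is about 7 weeks. From 3 months to 1 year is 12 − 3 = 9 months. The last interval is the longest, and a phone contact at 1 year has to cover all of it.

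5. **Size.** The documents give no admission rate. Suppose, purely as an assumption, that a share p of the 130 planned participants has an admission they do not link to the pelvis, and that the other routes catch a share k of these. The number missed is then 130 × p × (1 − k).
   - With p = 2%: 130 × 0.02 = 2.6 before allowing for k.
   - With p = 10%: 130 × 0.10 = 13 before allowing for k.
   - The documents do not fix k. If k = 1 nothing is missed; if k = 0 the figures are about 3 to 13. The possible range is therefore 0 to 13, which is too wide to serve as an estimate.

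**The case against.** The strongest reply is that the interview is one route among several. A reader might infer that admissions for heart attack or stroke are screened out before any investigator sees them, and that reportable events are therefore lost. The documents do not support that. The complications item carries no relatedness limit, the treating surgeon completes the evaluation at clinic visits, and serious events may be picked up at any contact. Staff who phone a participant are also meant to gather what visit data they can, which includes complications. This part of the objection stands: the item is a weak prompt, but it does not shut events out.

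Several further points also stand, in whole or in part.

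- The interview list is a summary, and the forms are an attachment outside the public text. The question on the form may already be unrestricted, as the Appendix B row suggests. That is a reason to align the two descriptions, since a reader cannot tell which one governs.
- A reader might set the item against the rule that relatedness is the local investigator's to judge. That rule, "if in the opinion of the local investigator, the research procedures more likely than not caused the harm", is a test for prompt reporting of new information and concerns the research procedures, not the pelvic injury. It does not contradict the interview item. That the patient ends up deciding relatedness is a fair inference from the wording, but no text says so.
- The serious adverse event section sets a reporting duty and does not make the interview its collection tool. The two differ in scope without being in strict contradiction.
- A reader might expect operated patients to link later admissions to the pelvis more readily, so that recording differs by arm. That is possible in an open trial, but nothing in the documents shows it or its direction.
- The restriction has a plausible purpose. Polytrauma patients are eligible, many readmissions may concern other injuries, and a pelvis-specific item tracks later pelvic surgery and crossover. A separate relatedness field would keep that information.

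**Conclusion.** The concern holds in a limited form. The interview item is narrower than the Appendix B row and than the range of serious events the protocol requires to be reported, and it suits the named systemic risks poorly because it refers to the injury. The other routes reduce the gap without closing it. What remains is mainly phone follow-up and admissions to other hospitals, above all over the 9 months before the 1-year visit.

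The number of events missed cannot be derived from the documents. The conclusion assumes that the form follows the interview list as written. If the form follows Appendix B, only the protocol text needs correcting. This is a worthwhile correction to safety data collection; it does not show that events are lost or that a treatment comparison is biased.

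**What to change.** Reword the item in the Follow-up Interviews list so that it covers every re-hospitalization and every operation since the last visit, whatever the cause, with the date and the reason. Add a separate field in which the investigator records relatedness, so that pelvis-related stays can still be pulled out for crossover and revision surgery. Check that the patient follow-up forms, Appendix B and the serious adverse event categories then agree.

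The cost is one reworded question and a few added fields. The downside is extra classification work for unrelated admissions, including planned ones and those for other injuries in polytrauma patients. No endpoint, sample size or analysis changes.
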